Official Title: Vascular Impairment in Type II Diabetes Mellitus with Co-morbid Obstructive Sleep Apnea

ClinicalTrials.gov ID (NCT number): NCT01629862

Statistical Analysis Plan Date: 01/05/2018

For the cross-sectional analysis of those with diabetes, sleep apnea, both, or neither, we will first use analysis of covariance to determine whether there is any interactive effect of sleep apnea and diabetes on our primary outcome (flow mediated dilation) as well as the three secondary outcomes (nitroglycerin-induced dilation, acetylcholine-induced skin blood flow, and sodium nitroprusside-induced skin blood flow) after controlling for age, sex, and body mass index (BMI). If a significant interaction is identified, the main effects of diabetes, sleep apnea, and their interaction will be reported using multivariable linear regression adjusting for age, sex, and BMI. If the interactive effect of sleep apnea and diabetes is not significant ($\alpha=0.05$), we will ignore any interaction and examine the additive effects of diabetes and sleep apnea on each outcome using multivariable linear regression adjusting for age, sex, and BMI. Using post-hoc contrasts, we will then further test for differences between those having both diabetes and sleep apnea alone versus those with diabetes alone and those with sleep apnea alone. All tertiary outcomes will be assessed in a similar fashion.

For the randomized clinical trial analysis, the primary outcome is percent change in flow mediated dilation (post-treatment minus pre-treatment divided by pre-treatment) with percent change in nitroglycerin induced dilation, acetylcholine induced skin blood flow and sodium nitroprusside induced skin blood flow as secondary outcomes. The primary analysis will be based on the use of unpaired t-tests to compare each outcome in those randomized to CPAP versus sham-CPAP using an intention to treat principle and $\alpha =0.05$. All tertiary outcomes will be assessed in a similar fashion. If significant differences ($\alpha =0.05$) are identified in key covariates (age, sex, BMI) between those randomized to CPAP and sham CPAP, secondary analyses will adjust for those covariates that significantly differ.

For all analyses, we will also report effect sizes with 95% confidence intervals to establish the size of our effects of interest.

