Official Title: Vascular Impairment in Type II Diabetes Mellitus with Co-Morbid Obstructive Sleep Apnea

ClinicalTrials.gov ID (NCT number): NCT01629862

Protocol Date: 4/28/2017

**PARTNERS HUMAN RESEARCH COMMITTEE
PROTOCOL SUMMARY**

Answer all questions accurately and completely in order to provide the PHRC with the relevant information to assess the risk-benefit ratio for the study. Do not leave sections blank.

PRINCIPAL/OVERALL INVESTIGATOR

[name]

PROTOCOL TITLE

Vascular impairment in type II diabetes mellitus with co-morbid obstructive sleep apnea

FUNDING

National Institutes of Health (NIH) R01-HL110350; American Heart Association (AHA) 14SDG20160000.

VERSION DATE

Version 27; 28 April 2017

SPECIFIC AIMS

Concisely state the objectives of the study and the hypothesis being tested.

Although both diabetes mellitus (DM) and obstructive sleep apnea (OSA) have adverse effects on endothelial function, it is not clear whether these two conditions diverge regarding their action on the vascular smooth muscle cell and various inflammatory pathways. We will investigate the interaction between diabetes mellitus (DM) and obstructive sleep apnea (OSA) on vascular functioning by performing a two-part study.

Aim 1: To compare the vascular physiology of matched controls, patients with DM alone, patients with OSA alone, and patients with DM+OSA. We hypothesize that OSA and DM will demonstrate a synergistic effect on cardiovascular risk, demonstrated by patients with DM+OSA displaying impaired vascular reactivity compared with patients with DM or OSA alone.

Aim 2: In a 3-month, double blinded randomized controlled trial, to compare the vascular physiology of patients with both DM and OSA, receiving either active continuous positive airway pressure (CPAP) or sham-CPAP. We hypothesize that patients treated with active CPAP will show significant improvements in vascular reactivity compared with those assigned sham-CPAP.

BACKGROUND AND SIGNIFICANCE

Provide a brief paragraph summarizing prior experience important for understanding the proposed study and procedures.

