The obesity pandemic has led to the increased prevalence of major complications including DM and OSA. Various studies have shown important improvements in the vascular complications of DM, however refinements in glycemic control have not always led to improvements in the macrovascular complications of DM. Thus, some have suggested that alternative therapeutic pathways need to be targeted to lower vascular complication rates further.

One such potential target is OSA. OSA is highly prevalent (up to 86%) in obese people with DM, and yet only a fraction of these patients are currently being diagnosed, and even fewer are currently receiving therapy for OSA. OSA has been established as a significant cardiovascular risk factor independent from co-morbidities including DM. However, there is a possibility that there may be interactions between DM and OSA, such that vascular risk may be increased by both conditions, or that the overall risk may be limited by ceiling effects of the two diseases.

Previous research conducted by the PI and co-investigators has established that OSA subjects have impaired macrovascular functioning compared to both lean and obese controls, but similar to lean and obese patients with DM. In contrast, microvascular functioning in the OSA subjects was shown to be similar to the lean and obese controls and higher than the lean and obese DM patients. Various inflammatory cytokines were also shown to be expressed to a greater degree in OSA patients compared with both controls and DM patients. Hence, although both OSA and DM affect endothelial function, the conditions may diverge regarding their action on the vascular smooth muscle cell and inflammatory pathways.

RESEARCH DESIGN AND METHODS

Briefly describe study design and anticipated enrollment, i.e., number of subjects to be enrolled by researchers study-wide and by Partners researchers. Provide a brief summary of the eligibility criteria (for example, age range, gender, medical condition). Include any local site restrictions, for example, "Enrollment at Partners will be limited to adults although the sponsor's protocol is open to both children and adults."

As mentioned under 'Specific Aims' above, the study consists of a cross-sectional study followed by a 3-month, double-blinded randomized controlled trial. All subjects will be enrolled by Partners researchers; there are therefore no local site restrictions.

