For Aim 1 (cross-sectional study), we plan to enroll four groups of 40 subjects each: healthy controls, patients with OSA alone, patients with DM alone, and patients with DM+OSA. All four groups will be matched for age, gender, and body mass index (BMI), as well as duration of DM where appropriate.

For Aim 2 (randomized controlled trial), we plan to enroll 55 patients with DM+OSA. Data for all of these patients will be included in Aim 1, with additional data to be collected for Aim 2.

Inclusion Criteria

All patients: ≤70 years of age, weight ≤450 pounds (the maximum supported by the cardiac magnetic resonance (CMR) imaging table).

OSA patients: Respiratory disturbance index (RDI) ≥10 and <100 events/hour determined during two consecutive home sleep studies; no evidence of non-OSA sleep disorders, Epworth Sleepiness Scale (ESS) score ≤18 (/24) indicating normal/moderate daytime sleepiness levels, no history of motor vehicle accident/s or near-miss accident/s related to sleepiness within the previous two years; not a commercial driver; naïve to CPAP treatment; not currently receiving treatment of any kind for OSA.

DM patients: A clinical diagnosis of type 2 DM; glycated hemoglobin (HbA1c) <8.0% indicating stable glycemic control.

Healthy controls: Normal fasting plasma glucose (<100 mg/dl); RDI<10 events/hour determined during two consecutive home sleep studies; no evidence of any other sleep disorder/s.

Exclusion Criteria

All patients: Hematocrit <32, metallic implants or other contraindication of CMR; pregnancy; collagen vascular disease; hepatic or renal disease; cardiopulmonary disease; use of medications that could affect sleep/breathing, or that could interact with nitroglycerin, non-English speakers.

Briefly describe study procedures. Include any local site restrictions, for example, “Subjects enrolled at Partners will not participate in the pharmacokinetic portion of the study.” Describe study endpoints.

The study procedure for Aim 1 (visits 1-2) will be the same for all four subject groups (healthy controls, OSA patients, DM patients, OSA+DM patients). Patients enrolling in Aim 2 will first complete Aim 1 (visits 1-2) followed by Aim 2 (visits 3-6).

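### Aim 1's stated sign of synergy is also met by additive effects, and the SAP explicitly promises the diabetes-by-apnea interaction only when it is significant

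*SAP*

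**What the plan says.** **Protocol, Specific Aims, Aim 1.** The hypothesis is a "synergistic effect on cardiovascular risk, demonstrated by patients with DM+OSA displaying impaired vascular reactivity compared with patients with DM or OSA alone".

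**Protocol, Background and Significance.** The two diseases may interact, such that "vascular risk may be increased by both conditions, or that the overall risk may be limited by ceiling effects of the two diseases". Earlier work by the team found that "OSA subjects have impaired macrovascular functioning compared to both lean and obese controls, but similar to lean and obese patients with DM". For microvascular function, however, it found OSA close to controls.

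**Protocol, Research Design and Methods.** For Aim 1, "we plan to enroll four groups of 40 subjects each". Aim 2 plans 55 patients with both conditions, and their data also enter Aim 1, so that group may be larger than 40.

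**SAP, cross-sectional analysis.** An analysis of covariance adjusted for age, sex and BMI first tests the interaction on flow-mediated dilation (FMD) and three secondary outcomes. Then: "If a significant interaction is identified, the main effects of diabetes, sleep apnea, and their interaction will be reported". If the test is not significant at 0.05, "we will ignore any interaction and examine the additive effects of diabetes and sleep apnea on each outcome". Next: "Using post-hoc contrasts, we will then further test for differences between those having both diabetes and sleep apnea alone versus those with diabetes alone", and likewise versus sleep apnea alone. The SAP closes: "For all analyses, we will also report effect sizes with 95% confidence intervals to establish the size of our effects of interest".

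**The concern.** Synergy means that the joint effect exceeds the sum of the separate effects. Aim 1's wording asks only that the joint effect exceed each separate effect, which is a much weaker condition. The SAP contains the right test, but its post-hoc contrasts are exactly the comparisons named in Aim 1, and nothing says which of the two settles the hypothesis. A report could follow both documents and present an additive, or partly ceiling-limited, result as synergy.

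The second issue is reporting. The interaction estimate is the quantity that bears on synergy or a ceiling. The SAP commits to it by name only after a significant test, and a test with low power will often be non-significant even when an interaction exists. A reader given only that outcome could mistake it for evidence of additivity.

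**Working it through.** The documents give no power, effect size or SD for Aim 1, so there is no planned figure to reproduce.

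**1. Algebra (no assumed effect size needed).** Write mean impairment as 0 (neither), D (DM), O (OSA) and D + O + I (both).
- Both versus DM alone: (D + O + I) − D = O + I.
- Both versus OSA alone: (D + O + I) − O = D + I.

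Both contrasts are positive whenever I > −min(D, O). That covers I = 0 (additive) and mildly negative I (sub-additive). On the additive scale only I measures synergy.

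**2. Precision of I.** Inputs: 40 per group (protocol); two-sided 0.05 (the SAP gives 0.05, two-sided is assumed); effects in residual-SD units (assumed); df = 160 − 4 groups − 3 covariates = 153.
- SE(I) = √(4/40) = 0.316 SD.
- 95% CI half-width = 1.976 × 0.316 = 0.62 SD.
- Noncentral-t power: 24%, 35% and 59% at I = 0.4, 0.5 and 0.7 SD. 80% power needs about 0.89 SD.

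With 55 in the DM+OSA group, SE = √(3/40 + 1/55) = 0.305, the half-width is 0.60 SD and power at 0.5 SD is 37%.

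**3. What a non-significant test tells the reader.** Take D = O = 0.5 SD. Equal effects fit the Background's macrovascular finding; the size is assumed.

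| Truth | Interaction non-significant |
|---|---|
| Full ceiling, I = −0.5 | 65% |
| Additive, I = 0 | 95% |
| Synergy, I = +0.5 | 65% |

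**4. How often the Aim 1 wording is met without synergy.** Entries are the share of studies in which DM+OSA is significantly worse than both single-condition groups (D = O = 0.5 SD, 40 per group). SE per contrast is √(2/40) = 0.224 SD from the four-group model and √(2/80) = 0.158 SD from the additive model. The two-stage rule uses four-group contrasts after a significant interaction and additive coefficients otherwise.

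| Truth | Four-group contrasts | Two-stage rule | Additive model alone |
|---|---|---|---|
| I = 0 | 44% | 76% | 78% |
| I = −0.2 | 13% | 46% | 51% |

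Under I = 0 the interaction test itself is significant in the harmful direction in only 5%/2 = 2.5% of studies.

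**5. Where OSA alone does nothing.** With D = 0.5, O = 0 and I = 0, worse than both occurs in 2.4% (four-group) or 2.9% (two-stage). The contrast against DM alone is then simply I, so Aim 1's wording nearly coincides with synergy.

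**The case against.** The strongest reply is that the SAP is the later document, tests the interaction first on the primary and secondary outcomes, labels its fallback additive and calls the group comparisons post hoc. This stands in part. A reader might infer that synergy is never tested or that the plan equates it with the contrasts, and the SAP does not support that. What remains is that Aim 1 still states the weaker rule and the SAP does not replace it.

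Second, the instruction to ignore the interaction may govern only which model is fitted, and "For all analyses, we will also report effect sizes with 95% confidence intervals to establish the size of our effects of interest" may cover the interaction test. That reading is tenable, so it cannot be said that the estimate will be withheld. But the sentence does not name the interaction, and it follows an instruction to ignore it.

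Third, reporting the CI cannot do everything. Its full width is about 2 × 0.62 = 1.25 SD, while the gap between I = −0.5 and I = +0.5 is 1.0 SD, so it will essentially never exclude both. The Background also raises a ceiling only as a possibility and does not set Aim 1 the task of separating it from additivity. Both points stand and limit what the fix can claim.

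Fourth, the 44% and 76% depend on the assumed effects and do not carry over to outcomes where OSA alone has little effect, as the Background suggests for microvascular function. This also stands.

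Finally, a reader might infer that the post-hoc contrasts come from the additive model and therefore carry inflated error under a ceiling. The SAP does not name the model, and its description of comparisons between patient groups fits a four-group model at least as well. This is only a request for clarification.

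**Conclusion.** The point holds. By algebra alone, the Aim 1 criterion does not distinguish synergy from additive or mildly sub-additive effects. The SAP does not say which result decides Aim 1, and its only explicit promise to report the interaction depends on significance.

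The size is illustrative, for FMD at D = O = 0.5 residual SD with 40 per group: 35% power for a 0.5 SD interaction, a CI half-width of 0.62 SD, and the criterion met in 44% of studies (four-group) or 76% (two-stage) when effects are exactly additive. These are true differences between groups, not false positives, and the error arises only if they are called synergy. The rate falls to 2–3% where OSA alone has no effect.

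This merits correction because it concerns how the central Aim 1 hypothesis is interpreted.

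**What to change.** 1. In the SAP, commit to reporting the DM x OSA interaction estimate with its 95% CI for every outcome, whatever its p-value, on a named analysis scale (for example absolute FMD), because interaction depends on scale. Base any statement about synergy or a ceiling on that estimate alone, and state that a non-significant test is not evidence of additivity.
2. Reword Aim 1 so that doing worse than either single-condition group is reported as added impairment, not as synergy.
3. As a clarification only, name the model behind the post-hoc contrasts. If the additive model was intended, moving to four-group contrasts has a price: SE 0.22 instead of 0.16 SD and, under additivity at 0.5 SD, power per contrast of 60% instead of 86% under the two-stage rule.

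Items 1 and 2 change wording and reporting only: no new data and no loss of power. They do not raise the power of the interaction test. With 40 per group the CI will usually be compatible with more than one of ceiling, additivity and synergy, and the report should say so.

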A co-investigator will accompany each subject to the BIDMC Microcirculation Laboratory where vascular testing will take place. Macrocirculation testing involves taking an ultrasound video of the brachial artery before and after a cuff is placed on the upper arm at supra-systolic pressure for five minutes, and before and after the administration of nitroglycerin. Microcirculation testing involves monitoring the blood flow of the forearm before and after the administration of acetylcholine and sodium nitroprusside. A licensed physician will then take two skin punch biopsies (used to evaluate potential changes in cellular proteins such as eNOS, P-eNOS, A20 or TNF-alpha, which may be up- or down-regulated with OSA and/or DM). Finally, DM patients will undergo a brief neuropathy evaluation.

All subjects will be provided with lunch, then accompanied to the BIDMC MRI Laboratory for a cardiac MRI scan.

Following the MRI, subjects will be accompanied to the BWH Shapiro Cardiovascular Center for optional exercise testing. Subjects will be asked to cycle for up to 30 minutes on an exercise machine until peak exercise, as determined by the patient, is reached. Heart rate and blood pressure will be monitored throughout. The exercise testing will add approximately 1 hour to Visit 2, when applicable.

Subjects enrolled in Aim 1 only (i.e. healthy controls, those with DM only, and those with OSA only), will finish the study at this point. The following visits are for subjects with DM+OSA who have consented to the 3-month randomized controlled trial.

- *Visit 3: Beginning of Run-In Phase*

Location: BWH Ambulatory Clinical Center or BWH Clinical Trial Center

Time Required: Approximately 30 minutes

Staff Responsible: Co-investigator

Subjects will be fitted with a mask and shown how to wear and clean it appropriately. If the subject finds the mask comfortable during this time, they will take it home and attempt to wear it while awake and/or asleep at home.

- *Visit 4: Randomization & Device Allocation*

Location: BWH Ambulatory Clinical Center or BWH Clinical Trial Center

Time Required: Approximately 1 hour

Staff Responsible: Co-investigator

Subjects who did not tolerate wearing the mask during the run-in phase will be excluded at this point.

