Eligible subjects will be randomized to the treatment arm (active CPAP) or placebo arm (sham CPAP) of the trial. All subjects will be given a device which can be set to sham CPAP, active CPAP, or auto-PAP. The devices are identical, and subjects will not be aware of the settings in their allocated device.

Those assigned to the active CPAP group will need to undergo a one-week titration procedure using auto-PAP in order to determine a therapeutic pressure for ongoing CPAP use; the device will be set to auto-PAP mode. Those assigned to the sham CPAP group will not need to undergo a titration; the device will be set to sham CPAP mode.

Time will be available for questions and troubleshooting, with emphasis placed on strategies to maximize adherence.

- *Visit 5: Beginning of Randomized Controlled Trial*

Location: BWH Ambulatory Clinical Center or BWH Clinical Trial Center

Time Required: Approximately 30 minutes

Staff Responsible: Co-investigator

All subjects will return after one week, when adherence data will be downloaded from each device.

Subjects who are to continue with sham CPAP will have their device returned to them with no changes, although they will not be aware as to whether the mode of treatment has been changed. Subjects assigned to the active treatment group will also have pressure information downloaded from their device. A co-investigator will analyze these data and decide on a suitable fixed CPAP pressure. The mode of the device will be changed to active CPAP at this pressure, but again, the subjects will not know whether the settings of the device have been changed.

Time will be available for questions and troubleshooting, with emphasis placed on strategies to maximize adherence.

Subjects will use their sham / active CPAP devices for the next three months at home. During this time, subjects will attend face-to-face meetings with an unblinded co-investigator as required and/or requested by the subject. Subjects will perform regular blood sugar checks as needed. It may be necessary for some subjects to undergo an additional home-based sleep study while using active or sham CPAP; advice will be sought by a licensed physician.

- *Visit 6: End-Trial Vascular Testing & Cardiac MRI*

Locations: BWH Ambulatory Clinical Center or BWH Clinical Trial Center (early morning), BIDMC Microcirculation Laboratory (mid-morning), BIDMC MRI Laboratory (late morning), BWH Shapiro Cardiovascular Center (early afternoon)

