Time Required: Approximately 5 hours

Staff Responsible: Licensed physician, ACC/CTC nursing staff, MRI technician, co-investigator

After three months of sham/active CPAP, subjects will return to the ACC or CTC in a fasting state. Adherence data will be downloaded from each device, followed by a repeat ECG measurement, questionnaires, pulse wave analysis, pregnancy testing and blood samples (approximately 90mL).

A co-investigator will accompany the subject to the BIDMC Microcirculation Laboratory for repeat vascular testing, skin biopsies, and a neuropathy evaluation.

All subjects will be provided with lunch, then accompanied to the BIDMC MRI Laboratory for a repeat cardiac MRI scan.

- *Post-Enrollment: CPAP Follow-Up*

Following Visit 6, a research assistant will access the medical record of each patient (either Beth Israel Deaconess Medical Center, or Brigham and Women's Hospital) to collect data regarding current CPAP use. If no data are found in the medical record, a research assistant will call each patient to gather this information over the phone.

The purpose of this follow-up is to investigate long-term engagement with sleep therapy following enrollment in a clinical trial. All patients who were recruited from sleep clinics were offered an appointment with their sleep specialist after study completion for ongoing sleep care. All patients who were recruited from other sources were offered a referral to a local sleep physician. We are interested in determining the rates of attendance at these clinical visits, and ascertaining whether there are differences in long-term CPAP usage by recruitment source.

For studies involving treatment or diagnosis, provide information about standard of care at Partners (e.g., BWH, MGH) and indicate how the study procedures differ from standard care. Provide information on available alternative treatments, procedures, or methods of diagnosis.

Patients with DM will already have a clinical diagnosis and will be well-established on treatment. We therefore do not suspect that we will identify any patients with undiagnosed DM. However, if this occurs, the primary care physician will be informed of the diagnosis with permission from the patient.

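### The randomized trial's primary endpoint divides by baseline FMD, with no rule for baselines at or below zero and no baseline covariate

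*SAP*

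**What the plan says.** In the SAP's paragraph on the randomized clinical trial, "the primary outcome is percent change in flow mediated dilation (post-treatment minus pre-treatment divided by pre-treatment". The three secondary outcomes (nitroglycerin-induced dilation and the two skin blood flow responses) are also percent changes. On the test, the SAP says: "The primary analysis will be based on the use of unpaired t-tests to compare each outcome", by intention to treat at alpha 0.05. Adjustment is confined to secondary analyses, and only if significant differences "are identified in key covariates (age, sex, BMI) between those randomized to CPAP and sham CPAP". Baseline FMD is not on that list. The closing paragraph adds that "we will also report effect sizes with 95% confidence intervals to establish the size of our effects of interest", without naming a scale.

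The protocol (Visit 2) describes macrocirculation testing as "taking an ultrasound video of the brachial artery before and after a cuff is placed on the upper arm". It gives no formula or unit for FMD. Under study procedures, "Patients enrolling in Aim 2 will first complete Aim 1 (visits 1-2) followed by Aim 2 (visits 3-6", so a baseline value is planned for every trial patient. The post-treatment value comes at Visit 6: "A co-investigator will accompany the subject to the BIDMC Microcirculation Laboratory for repeat vascular testing".

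Neither document says what to do when a baseline is zero, negative or close to zero.

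**The concern.** The plan divides by a quantity that is itself a before/after response. Dilation can be zero, and it can be negative if the artery narrows. The ratio then fails in three ways: it is undefined at zero, it reverses sign below zero, and it gives the lowest baselines the most weight. An intention-to-treat analysis cannot keep a patient with an undefined value without a rule, and dropping that patient conflicts with the principle. Any handling chosen after the data are seen could decide the primary result.

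Separately, dividing by baseline is not the same as adjusting for it. The planned Visit 2 measurement could reduce residual variance as a covariate, but the plan never uses it that way.

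This is the primary test of Aim 2, with 55 patients planned. The mask run-in may remove some before randomization.

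The zero and negative problem applies to FMD and nitroglycerin-induced dilation. How skin blood flow is quantified is not stated, so for those outcomes only the low-baseline weighting and the missing covariate are at issue.

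**Working it through.** **No figure to reproduce.** The documents give 55 planned trial patients (Research Design and Methods) but no power, expected effect, FMD mean or SD, or pre-post correlation. Visit 4 says only that "Eligible subjects will be randomized to the treatment arm (active CPAP) or placebo arm (sham CPAP) of the trial", with no allocation ratio. Everything below except the arithmetic in step 1 rests on assumptions.

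**Step 1: the formula, (post - pre)/pre.**
- Pre 0: undefined.
- Pre -1, post +1: (1 - (-1))/(-1) = -200%, although the patient improved.
- A gain of 2 points: 2/0.5 = +400%; 2/6 = +33%; 2/10 = +20%.

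Suppose all 28 patients of an arm gain exactly 2 points:
- all start at 6: mean +33%
- one starts at -1: (27 × 33.33 - 200)/28 = +25.0%
- three start at -1: (25 × 33.33 - 600)/28 = +8.3%
- one starts at 0.5: (27 × 33.33 + 400)/28 = +46.4%

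The benefit is identical in all four cases.

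**Step 2: how often a baseline is at or below zero.** For normal baselines the chance of at least one among 55 is 1 - (1 - Φ(-mean/SD))^55.

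| Assumed mean | SD 2 | SD 2.5 | SD 3 |
|---|---|---|---|
| 6 | 7% | 36% | 72% |
| 8 | 0.2% | 4% | 19% |

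Three or more in one arm of 28 is rare: 0.0008%, 0.15% and 2.5% at mean 6.

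**Step 3: power.** Simulation with 20,000 trials per setting, two-sided 0.05, 28 vs 27, mean 6, additive gain of 0.8 SD, pre-post correlation 0.4-0.6:

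| Baselines | Percent change | Change score | ANCOVA |
|---|---|---|---|
| Normal, SD 2-3 | 16-60% | 75-91% | 88-95% |
| Same, floored at 0.5 | 26-64% | 76-92% | 88-96% |
| Log-normal, CV 0.3-0.6 | 74-94% | 76-90% | 88-95% |

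Other allocations at correlation 0.5, percent change vs ANCOVA:
- 37 vs 18, either way round: 15-49% vs 87-88% (normal), 77-84% vs 87-88% (log-normal)
- 20 vs 20: 18-43% vs 80% (normal), 69-75% vs 80-82% (log-normal)

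With a fixed gain of 1.5 points, normal baselines and correlation 0.5 (10,000 trials per setting), power for percent change / change score / ANCOVA was:
- mean 6, SD 1.5: 84% / 96% / 99%
- mean 6, SD 3: 11% / 45% / 55%. Here the percent-change difference had the wrong sign in 31% of trials, against 2% for ANCOVA.

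**Step 4: settings that favour percent change.** With log-normal baselines and a gain of 1 point:

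| CV, correlation | Percent change | ANCOVA | Log-scale ANCOVA |
|---|---|---|---|
| 0.5, 0.8 | 65% | 55% | 75% |
| 0.5, 0.9 | 91.5% | 80% | 95% |
| 0.6, 0.9 | 87% | 68% | 92% |

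When effect and scatter were both proportional to baseline, percent change beat raw-scale ANCOVA in all 8 settings, by 3.5-9 points. Log-scale ANCOVA was at or above percent change in all 43 strictly positive settings tried, these included.

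**Step 5: the missing rule.** Three possible choices are to keep the signed ratio, divide by the absolute baseline, or drop the patient. At mean 6, among trials with a baseline at or below zero, these disagreed on significance in 47-58%, 33-44% and 28-35% (SD 2, 2.5, 3). Multiplying by the chances in step 2 gives the rate over all trials:
- SD 2: 0.07 × (0.47 to 0.58) = 3-4%
- SD 2.5: 0.36 × (0.33 to 0.44) = 12-16%
- SD 3: 0.72 × (0.28 to 0.35) = 20-25%

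Dropping the single patient with the smallest absolute baseline changed significance in 18-25% of trials (normal), 13-19% (floored) and 3-7% (log-normal), against 1-2% for ANCOVA.

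**Step 6: type I error.** As planned, 2.2-5.2%. Taking the best of the three choices in hindsight gives 3.8-4.3%. Also allowing baselines below 1 to be dropped gives 4.8-6.7%.

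**The case against.** The documents do not show that a baseline at or below zero will occur. Where the protocol's background calls vascular function impaired, it means relative to controls, and it also allows for a ceiling effect. The large power losses come from normal baselines with mass near zero and an additive gain that is 27-40% of the assumed mean (1.6/6 to 2.4/6). With log-normal baselines, percent change and change score are almost level, so most of the remaining gap is the ordinary gain from a baseline covariate. The planned test is valid, raw-scale ANCOVA is not uniformly better, and the choice between a relative and an absolute effect is partly preference. All of that stands, and it limits the size of the claim.

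It does not remove the claim. The low-baseline weighting needs no zero or negative values: with baselines floored at 0.5, percent change still had only 26-64% power. The missing rule and the missing covariate are plain from the text. Where a relative effect is wanted, log-scale ANCOVA did at least as well in every strictly positive setting tried.

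Two further cautions hold. That the confidence interval will be on the percent-change scale is the natural reading, but the SAP does not say so. And an amendment may come late: the protocol provides for an unblinded co-investigator during treatment and weekly review of all data, and it writes of completed patients in the past tense, although it also promises coded data for blinded analysis.

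**Conclusion.** The concern holds and should be fixed. Confidence is high that the endpoint is undefined at a zero baseline and sign-reversed at a negative one, that no rule covers such baselines, and that baseline FMD is never a covariate in the trial analysis. This assumes FMD means the dilation response, as its name and the before/after measurement indicate.

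The harm is lost power and an estimate that one patient's starting value can move, not a raised false-positive rate for the planned test. Its size depends on a distribution the documents do not give. It is large if baselines are roughly normal with a wide spread. It is modest if they are strictly positive and skewed, and there percent change can even beat raw-scale ANCOVA.

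**What to change.** Make the primary analysis an ANCOVA of post-treatment FMD on randomized arm with Visit 2 FMD as covariate, reporting the adjusted difference with its 95% confidence interval. Use the same model for the secondary outcomes. Keep percent change as a supportive or descriptive result, with a prespecified rule for baselines at or below zero. If a relative effect is wanted, use log-scale ANCOVA for outcomes that are strictly positive. Aim 2 speaks of improved vascular reactivity, not relative change, so an effect in absolute units still answers it.

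The cost is one residual degree of freedom and no new data, visits or patients. The headline effect moves from relative percent to FMD units. Some power is given up if baselines are positive and skewed with high pre-post correlation, or if effect and scatter are proportional to baseline. The change needs a dated SAP amendment before unblinding. If arms are already unblinded, report percent change as planned and label the ANCOVA a sensitivity analysis.
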